6.2 Administration

Study medication will be supplied in single-dose vials containing 0.20 mL (approximately 0.17 mL deliverable volume) per vial. A medication kit contains 6 pouches with 2 strips of 5 vials in each pouch, for a total of 60 vials and a plastic bag labelled with the kit number.

The first dose of the IMP should be administered by the investigator or a designated study team member at Visit 1. After that, the investigator or a designated study team member will remove 4 vials from the opened pouch. He or she will place the removed vials (used one and unused ones) in a bag provided with the kit and store them at the study site in a secure location for traceability. The remaining 5 vials will be returned to the medication kit, for dispensation to the patient. Finally, the patient will receive a kit with 55 vials for their self-administration in the study eye QID for 14 consecutive days.

6.2.1 Method of Assigning Patients to Treatment Groups

A total of 210 patients will be randomized 2:1 to the following 2 arms:

- 1. Clobetasol propionate ophthalmic nanoemulsion 0.05%: 140 patients
- 2. Placebo: 70 patients

Patients will be randomized into one of two arms, based on a computer-generated 2:1 ratio randomization schedule. A randomization number will be assigned to each patient in addition to the patient ID number.

The disclosure of the randomization schedule will be done when finishing the evaluation of the corresponding arm or in case it is needed to provide convenient medical care to any patient due to AEs.

6.2.2 Dose and Treatment Regimens in the Study

The IMP will be administered as ophthalmic treatment.

The proposed clinical posology is one drop (0.03 mL) of IMP into the affected eye QID for a 14-day treatment period. Doses should be administered approximately 6 hours apart.

This posology is selected based on pre-clinical data of clobetasol propionate ophthalmic micronized. Systemic HED in the rabbit study was 17-times higher compared to dosing in one eye of adults.

Accordingly, the suggested dose for this study is aligned with current efficacy and safety-proved doses of clobetasol.

If a patient's medication is lost by breakage or spillage, the investigator will retrieve the replacement medications and communicate to Sponsor. The reason why the replacement medication has been used should be documented on the eCRF "Comments Form".

6.3 Packaging, Labeling, and Storage

All IMP used in this study will be prepared, packaged, and labeled in accordance with the standard operating procedures (SOPs) of Good Manufacturing Practice (GMP) guidelines, International Conference on Harmonization (ICH) guidelines for Good Clinical Practices (GCP), guidelines for Quality System Regulations (QSR), and applicable regulations.

The IMP is manufactured by Crystal Pharma S.A.U., in compliance with the current USP correspondent monograph. The excipients used are commonly used in this kind of pharmaceutical preparations of ophthalmic nanoemulsions.

The primary packaging is a low-density polyethylene (LDPE) single-dose vial with a volume of approximately 0.20 mL (approximately 0.17 mL deliverable volume). As clobetasol propionate is known to be light-sensitive and the immediate container (vial) is semi-permeable, the vials will be contained in an aluminium foil overwrap pouch and a carton box for protection. Each

pack contains two strips of 5 single-use vials wrapped in a protective heat-sealed foil pouch. Each vial contains approximately 0.10 mg of clobetasol propionate. The dose is one drop (approximately 0.03 mL) that corresponds to 0.015 mg of clobetasol propionate.

The bulk product is prepared by dissolving the drug substance in the organic phase followed by addition of the aqueous phase until the nanoemulsion is formed. The other excipients are added in the preparation vessel and then transferred to holding tanks. The holding tanks are connected to the filling suite for blow-fill-seal process and packaging. The LDPE resin is extruded and molded, the bulk solution is aseptically filled, and the vial is completely sealed in one continuous automated process. The vials will be subsequently placed into an aluminum foil overwrap pouch and heat-sealed to protect the product.

Specifications have been established for the drug product and are controlled by the correspondent analytical methods developed specifically for clobetasol propionate ophthalmic nanoemulsion 0.05%.

Except for the change in manufacturing center, the supportive batches will be fully representative of the clinical trial batches. The clinical trial batches that will be manufactured at Laboratorios Salvat, S.A. will also be placed on stability and will be monitored at least over the duration of the study.

The containers will be relabeled as investigational drug.

To maintain the double-masking, the investigational product and placebo will be provided in packaging that will be identical in appearance and labeling. A label with "CLOBOF3-16IA01 Investigational Drug Product", or similar language, will be affixed to each pouch containing eye dropper vials and will include the appropriate instructions for storage.

Drug labels will comply with the legal requirements and will be printed in the language of each clinical center. All study drugs will be provided with labels indicating that the product is for investigational purpose only. The labels will include a code that ensures the masking, the protocol number, the storage conditions and all the details required by the applicable regulations.

The IMP will be stored in a secure area with limited access. The IMP should not be freeze. Other storage conditions will be observed as per the labelling instructions of the IMP.

6.4 Masking and Breaking the Mask

Clobetasol propionate ophthalmic nanoemulsion 0.05% and placebo will be identical in appearance and will be self-administered by the patients with identical schedules (QID for 14 days) in order to guarantee the double-masking conditions. The sample labels had no information that would allow identification of the treatment administered.

The masking system will be done by a website platform. All patients and treatments will be codified in the mentioned platform.

The investigator, Sponsor, patient and monitor involved in reporting, obtaining, and/or reviewing the clinical evaluations will not be aware of the treatment being administered in case of clobetasol and placebo arms. The double-masking of the clobetasol and placebo arms will be maintained throughout the conduct of the study. Only once all study data has been verified and the database locked, individual patients will be unmasked.

The study randomization should only be broken for valid medical or safety reasons, for example, a SAE where it is necessary for the investigator to know which treatment the participant is receiving to ensure the appropriate SAE treatment. In the event of an emergency, the investigator will have to decide on the necessity of unmasking the patient's treatment

assignment. The investigator will report about this event to the Sponsor as soon as possible. If unmasking occurs, the investigator must record the reason for unmasking, as well as the date and time of the event. Corresponding information will be recorded on the eCRF and will be documented in a note to file which will be filed in the Trial Master File.

6.5 Drug Accountability

The Sponsor has the responsibility of providing the IMP for free and perfectly identified and prepared in agreement with GMP's procedure.

The medication of the clinical trial only can be sent to the investigation center after having obtained all the applicable approvals (e.g. IRBs).

The IMP supplier will send the samples of medication to the Pharmacy Service of the study center together with the pertinent documentation (fundamentally, the analytical memory of the samples).

The Pharmacy Service is responsible of receiving the samples of medication, to verify and/or to assure that they follow the in-force legislation of labelling, to preserve them correctly and to send them to the study center after verifying that all the approvals have been obtained and the contracts have been signed.

The investigator, or the responsible investigator with delegated function, must assure the correct reception in the study center of the medication for the clinical trial (inventory of samples and review of the labelling) as well as his correct storage according to the specific procedure of conservation. The reception and storage of the medication in the study center will be documented properly according the guidelines established in the corresponding SOP.

The IMPs must be tracked using two logs:

- A center-specific log to track the complete inventory (that is, what is shipped between the center and the Sponsor)
- A patient-specific log to track what is dispensed to and returned by the patient. The
 investigator and the pharmacist, if applicable, must agree not to dispense any IMP to
 any person, except patients enrolled in the study. The investigator or the pharmacist (if
 applicable) must maintain an adequate record of the receipt and distribution of the
 IMPs. This log must be available for inspection at any time.

Patients will be instructed to return all single-dose vials, both used and unused, to the center at Visit 4 or at Early Termination Visit (if applicable), for which compliance will be assessed by the investigator or designee, utilizing the patient diary.

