The investigator will administer the first dose of IMP on Day 1 at the study center. Study medication will be then dispensed to patients for self-administration during the study at a dosage of one drop QID during 14 days.

[figure not shown]
Patients will be provided with diaries to record their daily dosing. Doses should be administered approximately 6 hours apart. In addition, patients will be asked to make note of any missed doses and the reason for the missed dosage. The intent is to capture missed doses, *per* se, rather than a shifted dosing schedule.

As this is a double-masked study, all patients, investigators, sub-investigators, and center personnel involved in measuring, monitoring and obtaining data in the study will be masked to patient treatment assignment. The study medication will be packaged in a masked fashion and will be administered and dispensed by the investigator according to patients' randomization numbers. In addition, all Sponsor's and vendors' personnel involved in the onsite monitoring and direct management of the data and study centers will remain masked to individual patient data.

Protocol waivers of exemptions are not allowed with the exception of immediate safety concerns. Therefore, adherence to the study design requirements, including those specified in the Table 1, are essential and required for study conduct.

Figure 3 Diagram of Study Design

^{*} Patients who, for any reason, withdraw from the study treatment will be highly encouraged to continue attending all their remaining study visits to collect the most complete efficacy and safety data.

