4.3.2.5 Visit 4 (Day 15 ± 2 days)

At Visit 4, the following activities and assessments will be performed (**NOTE**: All ocular assessments must be performed in both eyes):

- Eye pain (VAS) to be assessed prior to any physical evaluation
- Eye discomfort to be assessed prior to any physical evaluation
- Photophobia (VAS) to be assessed prior to any physical evaluation
- Vital signs examination (temperature, blood pressure and pulse) to be completed 15 min before any ocular assessment
- Slit-lamp examination
 - ✓ Anterior chamber cell
 - ✓ Anterior chamber flare
 - ✓ Chemosis
 - ✓ Bulbar conjunctival injection
 - ✓ Ciliary injection
 - ✓ Corneal edema
 - ✓ Keratic precipitates
- IOP
- BCVA measured by Snellen chart
- Indirect ophthalmoscopy
- Review and return of the patient diary
- Return of the remaining study medication
- AE assessment (**NOTE**: Expected changes or the presence of inflammation or pain resulting from routine cataract surgery will not be captured as AEs)
- Concomitant medications

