4.3.2.6 Visit 5 (Day 29 ± 2 days)

At Visit 5, the following activities and assessments will be performed (**NOTE**: All ocular assessments must be performed in both eyes):

- Eye pain (VAS) to be assessed prior to any physical evaluation
- Eye discomfort to be assessed prior to any physical evaluation
- Photophobia (VAS) to be assessed prior to any physical evaluation

- Vital signs examination (temperature, blood pressure and pulse) to be completed 15 min before any ocular assessment
- Slit-lamp examination
 - ✓ Anterior chamber cell
 - ✓ Anterior chamber flare
 - ✓ Chemosis
 - ✓ Bulbar conjunctival injection
 - ✓ Ciliary injection
 - ✓ Corneal edema
 - ✓ Keratic precipitates
- IOP
- BCVA measured by Snellen chart
- Indirect ophthalmoscopy
- AE assessment (**NOTE**: Expected changes or the presence of inflammation or pain resulting from routine cataract surgery will not be captured as AEs)
- Concomitant medications

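### An in-window Visit 4 on Day 13 or 14 collects all vials and the diary before the 56-dose course is finished (minor; Day 8 endpoints not affected)

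*Protocol*

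**What the plan says.** **Course.** Protocol 4.1: "The investigator will administer the first dose of IMP on Day 1 at the study center". Section 6.2 adds that "the patient will receive a kit with 55 vials for their self-administration in the study eye QID for 14 consecutive days", and section 6.2.2 gives the spacing: "Doses should be administered approximately 6 hours apart". SAP 6.3.8 fixes the planned doses at 56.

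**Visit.** Protocol 4.3.2.5 is headed "Visit 4 (Day 15 ± 2 days", so Days 13 to 17 are all in window. The same window appears in the synopsis, section 4.1 and Table 1.

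**Returns.** The Visit 4 list includes "Review and return of the patient diary" and "Return of the remaining study medication". Section 6.5 is broader: "Patients will be instructed to return all single-dose vials, both used and unused, to the center at Visit 4" (or at an Early Termination Visit). Table 1 places these returns only at Visit 4 and at early termination. The list for "Visit 5 (Day 29 ± 2 days" contains neither.

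Nothing in either document requires Visit 4 to follow the last dose, lets a patient seen early keep vials or diary, or provides for giving them back.

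**The concern.** The early half of the Visit 4 window overlaps the treatment period, and the return step has no exception for that overlap. A site can keep every visit-level instruction and still stop treatment one or two days short. At stake are:

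- the total exposure received;
- the compliance table on the fixed 56-dose denominator, where the 100% category is out of reach for such a patient;
- the last pain scores in the diary, which feed a listed secondary endpoint (Protocol 7.3);
- the Day 15 efficacy results (exploratory under SAP 6.3.6.2) and the descriptive Day 15 intraocular pressure, which would combine patients part-way through the course with patients who have completed it.

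**Working it through.** **Inputs.** First dose on Day 1 (Protocol 4.1); 55 vials for home use (6.2); doses about 6 hours apart (6.2.2); visits at roughly the same time of day (4.1); Visit 4 on Days 13 to 17 (4.3.2.5); 56 planned doses (SAP 6.3.8); non-compliance below 80% (SAP 5).

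**The plan's own figure.** 1 + 55 = 56 and 4 × 14 = 56. Both agree with the SAP.

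**Doses due before Visit 4.** Put the first dose at 0 h. Dose k is due at 6 × (k − 1) h, so dose 56 is due at 6 × 55 = 330 h. A visit on Day d at the same clock time falls at 24 × (d − 1) h, and 4 × (d − 1) doses come before it, capped at 56.

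| Visit 4 on | Hours after first dose | Doses taken | Doses lost | Compliance on 56 |
|---|---|---|---|---|
| Day 13 | 288 | 48 | 8 | 85.7% |
| Day 14 | 312 | 52 | 4 | 92.9% |
| Day 15 | 336 | 56 | 0 | 100% |
| Days 16–17 | 360–384 | 56 | 0 | 100% |

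The part of the course cut off is 330 − 288 = 42 h on Day 13 and 330 − 312 = 18 h on Day 14.

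**Sensitivity to clock time.** A visit 4 h later in the day gives 49/56 = 87.5% on Day 13 and 53/56 = 94.6% on Day 14. A visit 4 h earlier leaves 48 and 52 unchanged.

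**Wider range.** The documents do not state how many doses fall on Day 1. Assume d1 = 1 to 4 on Day 1, v = 0 to 3 on the visit day before the visit, and 4 on each day between. Doses taken are d1 + 4 × (d − 2) + v, capped at 56:

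- Day 13: 44 + d1 + v = 45 to 51 (80.4% to 91.1%).
- Day 14: 48 + d1 + v = 49 to 55 (87.5% to 98.2%).
- Day 15: 52 + d1 + v = 53 to 56 (94.6% to 100%).

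**The 80% line.** 0.80 × 56 = 44.8, so 45 doses are needed. From 48 doses a patient can miss three more (45/56 = 80.4%); a fourth crosses the line (44/56 = 78.6%). From 52 doses, seven more misses are tolerated.

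**The SAP's second measure.** Compliance at the last visit on treatment divides by (end date − first date + 1) × 4. In the same-clock-time case on Day 13, this gives 48/(13 × 4) = 92.3% if any dose is taken on the visit day, or 48/(12 × 4) = 100% if none is. A patient with 1 to 3 doses on Day 1 who takes all 56 finishes on Day 15 and scores 56/(15 × 4) = 93.3%. This measure therefore largely absorbs an early stop, but it restores no dose or diary entry.

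**The case against.** The strongest reply is that the protocol prescribes a full 14-day course in several places and calls adherence to the design essential (4.1). The Visit 4 target is the day after that course, so a site that books after the last dose satisfies every rule. That is correct, and a reader who infers that the documents contradict themselves goes too far. It is a gap: the early days are also permitted, and the return rule says nothing about unfinished treatment.

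A second reply is that the effect on compliance is modest and already partly handled. This also stands. The last-visit measure adjusts its denominator for an earlier end date. A reader might infer that an early visit leaves patients one missed dose from non-compliance. That needs the 45-dose extreme: a single dose on Day 1 and none before the visit on Day 13, which means a late Visit 1 and an early Visit 4. Section 4.1 asks for visits at about the same time of day, and on that basis the starting point is 48 doses, with three further misses tolerated.

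A reader might also infer damage to the main results. The documents do not support that. The primary and key secondary endpoints are read at Day 8, and their per-protocol set uses compliance at Visit 3 against 32 planned doses (SAP 5 and 6.3.8). Both arms share the schedule under masking, so nothing here points to bias between arms. SAP 6.3.6.2 does mention per-protocol checks of secondary endpoints, but the readable rows of the SAP's table list show a per-protocol set only for the two Day 8 analyses.

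**Conclusion.** The point holds as a minor schedule gap. An in-window Visit 4 on Day 13 or 14, with the return rule followed, costs a fully adherent patient 8 or 4 of 56 doses and the matching last diary entries; from Day 15 nothing is lost. These figures assume 6-hourly dosing and a visit at the clock time of the first dose. The early visit alone does not take an otherwise adherent patient below 80%, even at the edge of the wider range. The consequences are confined to exposure, descriptive compliance, late diary pain scores, and exploratory or descriptive Day 15 results. The documents do not say how many patients would be seen early, so no trial-level effect can be put on it.

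**What to change.** 1. Make Visit 4 one-sided, Day 15 + 2 days, in the synopsis, section 4.1, Table 1 and section 4.3.2.5. Visit 2 already has this form (Day 3 + 1 day). This is the change that stops Day 15 assessments from being made mid-course; letting patients keep their vials would not do that.
2. State in 4.3.2.5 and 6.5 that dosing and diary entries continue through the 56th dose, and that vials and diary are returned only after it. If Visit 4 comes first, they are returned at Visit 5 or by a drop-off. This covers early visits that still occur, and a Day 15 visit held earlier in the day than the first dose, where up to 3 doses could remain under the wider assumptions.

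The cost is a few lines of text, a 3-day instead of a 5-day visit window, and an occasional later return of vials and diary.

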6.6 Compliance

Compliance will be assessed by comparing study product accountability records with the dosing information recorded daily by the patients in the patient diaries. The center will document this comparison along with verification of the numbers of used and unused study product single-dose vials. The numbers of missed doses as assessed at each clinic visit should be documented in the eCRF as per the patient diary.

Patients' diaries will be reviewed by the study staff at each study visit during the treatment period.

6.7 Prior and Concomitant Medications

All medications (including OTC, vitamins, and antacids) taken 2 months prior to Screening visit (Visit -1) (36 months prior for ocular implants and/or intravitreal injections) and throughout the study duration, must be recorded on the eCRF. The generic name of the drug, dose, route of administration, duration of treatment (including start and stop dates), frequency, indication, and whether or not the medication was taken due to an AE will be recorded for each medication.

Patients will be asked to phone the study center at any time to speak to a member of the medical personnel should they require any concomitant medication.

Medication, which is considered necessary for the patient safety and well-being, may be given at the discretion of the investigator. However, concomitant medication administered during the study may lead to withdrawal of the patient from the IMP (Section 6.7.1).

6.7.1 Prohibited Concomitant Medications

The use of the following medications is not permitted during the study:

- Any systemic or local therapy with corticosteroids (other than the study drug) or immunosuppressant (except pre-surgical and/or surgical administration of 1 drop of a topical NSAID or corticosteroid, at the investigator discretion)
- Any topical ocular medication (except preservative-free antibiotics for prophylactic purposes and preservative-free artificial tears).
- Any systemic NSAID or opioids drugs (except occasional use of OTC formulations titrated no more than one single dose per week)

The aforementioned medications will be considered as rescue medications when administered in patients not responding to the IMP (Section 6.7.2).

6.7.2 Rescue Medication

Any patients not responding adequately to the IMP may be rescued and placed on alternate therapy (Section 6.7) at the investigator's discretion at any time.

The choice of rescue medication is at the investigator's discretion. Any patient placed on rescue therapy will discontinue the use of the IMP and the investigator must made extensive efforts to ensure that the patient will attend all his/her remaining study visits until study completion, aiming to collect the most complete efficacy and safety data.

Additionally, patients will be asked to phone the study center at any time to speak to a member of the medical personnel should they experience any worsening of ocular conditions or other AFs

Rescued patients will be considered treatment failures, but the need for rescue therapy will not be considered an AE.

6.8 Medical Care of Patients after the End of the Study

Clobetasol propionate ophthalmic nanoemulsion 0.05% is an IMP under development and will consequently not be available for treatment of the patients after study completion.

After their participation in the study, patients will continue treatment in accordance with the study center's clinical practice guidelines and standard of care.

7. ASSESSMENTS OF EFFICACY

The timings of the assessments are described in Section 4.3.1 and Table 1.

